Appendix 1. Abbreviations

The following is a list of abbreviations that may be used in the protocol.

Abbreviation	Term
7vPnC	7-valent pneumococcal conjugate vaccine
13vPnC	13-valent pneumococcal conjugate vaccine
ACIP	Advisory Committee on Immunization Practices
AE	adverse event
ALT	alanine aminotransferase
AST	aspartate aminotransferase
CBER	Center for Biologics Evaluation and Research
CI	confidence interval
CK	creatine kinase
COPD	chronic obstructive pulmonary disease
CRF	case report form
CRM ₁₉₇	cross-reactive material 197 (nontoxic variant of diphtheria toxin)
CSA	clinical study agreement
CSF	cerebrospinal fluid
CT	clinical trial
DILI	drug-induced liver injury
DMARD	disease-modifying antirheumatic drug
EC	ethics committee
e-diary	electronic diary
EDP	exposure during pregnancy
EU	European Union
EudraCT	European Clinical Trials Database
FDA	Food and Drug Administration (United States)
FSFV	first subject first visit
FSH	follicle-stimulating hormone
GCP	Good Clinical Practice
GGT	gamma-glutamyl transferase
GMC	geometric mean concentration
GMFR	geometric mean fold rise
GMT	geometric mean titer
GVHD	graft-versus-host disease
hCG	human chorionic gonadotropin
HIV	human immunodeficiency virus
HSCT	hematopoietic stem cell transplant
ICH	International Council for Harmonisation
ID	identification
IgG	immunoglobulin G
IND	investigational new drug application
INR	international normalized ratio
IPD	invasive pneumococcal disease
IRB	institutional review board

PF-05208760, 13-valent Pneumococcal Conjugate Vaccine
 B1851172
 Final Protocol, 20 March 2018

Abbreviation	Term
IUD	intrauterine device
IWR	interactive web response
LFT	liver function test
LSLV	last subject last visit
MedDRA	Medical Dictionary for Regulatory Activities
N/A	not applicable
NSAID	nonsteroidal anti-inflammatory drug
OPA	opsonophagocytic activity
PCD	primary completion date
PD	pneumococcal disease
PI	principal investigator
PPSV23	23-valent pneumococcal polysaccharide vaccine
PT	prothrombin time
RCDC	reverse cumulative distribution curves
SAE	serious adverse event
SAP	statistical analysis plan
SCD	sickle-cell disease
SRM	study reference manual
SRSD	single reference safety document
SUSAR	suspected unexpected serious adverse reaction
TBili	total bilirubin
UI	uncertainty interval
ULN	upper limit of normal
US	United States

## 1. VERSION HISTORY

This statistical analysis plan (SAP) for Study B1851172 is based on the protocol dated 20 Mar 2018.

**Table 1. Summary of Major Changes in SAP Amendments**

SAP Version	Author(s)	Change	Rationale
1.0	PPD [REDACTED]		
2.0	PPD [REDACTED]	Table 2 OPA LLOQs for serotype 7F and 9V were modified.	For update to most current version
		Section 6.1.1.5. Adverse Events, Endpoints Added description of subgroups	Omission
		Section 6.1.1.5, Adverse Events, Reporting summaries Deleted “Number(%) of Subjects With Adverse Events”	Erroneous description
		Section 6.1.1.5. Adverse Events, Reporting summaries Summary table for “Severe and Life-Threatening AE” was divided into for “Severe AE” and “Life-Threatening AE”.	To clarify summarized results
		Section 6.1.1.5, Adverse Events, Reporting summaries Added the following items: 
 
✓ Adverse Event Leading to Discontinuation
 
✓ Related Adverse Event Leading to Discontinuation
 
✓ Immediate Adverse Events
 
✓ Related Immediate Adverse Events
 
✓ Deaths
 
✓ Related Deaths
 
	Omission
		Section 6.5.2. Baseline Summaries (Demographic, Medical History) For medical history summary, analysis population was changed from safety population to all enrolled subjects.	Discussion with the clinician for this study.

090177e190dcce77ApprovedApproved On: 06-May-2019 11:24 (GMT)

**Table 1. Summary of Major Changes in SAP Amendments**

SAP Version	Author(s)	Change	Rationale
		
Section 6.5.6. Immunosuppressive Drug, Immune-Modifying Drugs, and/or Monoclonal Antibody                      Analysis population was changed from safety population to all enrolled subjects.
	
Discussion with the clinician for this study.

**2. INTRODUCTION**

This SAP provides the detailed methodology for summary and statistical analyses of the data collected in Study B1851172. This document may modify the plans outlined in the protocol; however, any major modifications of the primary endpoint definition or its analysis will also be reflected in a protocol amendment.

090177e190dcce77\Approved\Approved On: 06-May-2019 11:24 (GMT)

## 2.1. Study Objectives

Primary Objective:	Primary Endpoints:

 
To assess the safety and tolerability of a single dose of 13-valent pneumococcal conjugate vaccine (13vPnC) as measured by the incidence of local reactions, systemic events, adverse events (AEs), and serious adverse events (SAEs).
 
	
 
Number and proportion of subjects reporting local reactions (redness, swelling, pain at injection site) and severity of the local reactions occurring within the 7-day period following study vaccination in the 6- to <18-year age group.
 
Number and proportion of subjects reporting local reactions (redness, swelling, pain at injection site) and severity of the local reactions occurring within the 14-day period following study vaccination in the 18- to <65-year age group.
 
Number and proportion of subjects reporting systemic events (fever, fatigue, headache, vomiting, diarrhea, muscle pain, joint pain) and severity of the systemic events occurring within the 7-day period following study vaccination in the 6- to <18-year age group.
 
Number and proportion of subjects reporting systemic events (fever, fatigue, headache, vomiting, diarrhea, muscle pain, joint pain) and severity of the systemic events occurring within the 14-day period following study vaccination in the 18- to <65-year age group.
 
Number and proportion of subjects reporting AEs and SAEs until Visit 2 categorized according to the Medical Dictionary for Regulatory Activities (MedDRA) in all age groups.
 

Secondary Objective:	Secondary Endpoints:

 
To describe the immune responses elicited by a single dose of 13vPnC.
 
	
 
Serotype-specific opsonophagocytic activity (OPA) geometric mean titers (GMTs) 1 month after vaccination in all age groups.
 
Geometric mean fold rises (GMFRs) in serotype-specific OPA titers from before vaccination to 1 month after vaccination in all age groups.
 
Serotype-specific immunoglobulin G (IgG) geometric mean concentrations (GMCs) 1 month after vaccination in all age groups.
 
GMFRs in serotype-specific IgG from before vaccination to 1 month after vaccination in all age groups.
 

090177e190dcce77ApprovedOn: 06-May-2019 11:24 (GMT)

## 2.2. Study Design

This is a Phase 3, multicenter, single-arm, open-label study to assess the safety, tolerability, and immunogenicity of a single dose of 13vPnC in Japanese subjects aged 6 to 64 years who are considered to be at increased risk of pneumococcal disease and who are naive to pneumococcal vaccines.

This study consists of 2 age groups, 6 to <18 years old and 18 to <65 years old. Subjects will be enrolled in 1 of these age groups and will be assigned a container number of investigational product by an interactive web response (IWR) system. For the purposes of subject participation in the study, including data collection procedures, enrollment in the study is considered to occur at the time of investigational product assignment.

### Approximate Duration of Subject Participation

Subjects will participate in the study for approximately 1 month (29 to 43 days).

### Approximate Duration of the Study

The study will be completed in approximately 6 months. Study duration is from first subject first visit (FSFV) to last subject last visit (LSLV).

### Approximate Number of Subjects

Approximately 200 subjects will be enrolled: approximately 50 subjects in the 6- to <18-year age group and approximately 150 subjects in the 18- to <65-year age group.

For the purpose of ensuring a minimum number of subjects in each of the age categories, at least 15 subjects aged 6 to <12 years (children) and 15 subjects aged 12 to <18 years (adolescents) will be enrolled within the 6- to <18-year age group. Furthermore, at least 50 subjects aged 18 to <50 years (young adults) and 50 subjects aged 50 to <65 years (older adults) will be enrolled within the 18- to <65-year age group.

## 3. ENDPOINTS AND BASELINE VARIABLES: DEFINITIONS AND CONVENTIONS

### 3.1. Primary Endpoints

See [Section 2.1](#).

### 3.2. Secondary Endpoints

See [Section 2.1](#).

### 3.3. Other Endpoints

Not applicable (N/A).

### 3.4. Baseline Variables

The demographic and baseline characteristics include sex, race, ethnicity, smoking status, and age at the time of vaccination. Age at the time of vaccination is the only demographic variable that needs to be derived. This variable is derived as  $(\text{vaccination date} - \text{date of birth} + 1) / 365.25$  and truncated to the nearest integer.

Smoking status, as either smoker, ex-smoker, or never smoked during the 6 months prior to the study participation, will be obtained from the case report form (CRF).

### 3.5. Safety Endpoints

Safety endpoints are the primary endpoints. See [Section 2.1](#).

## 4. ANALYSIS SETS

Data for all subjects will be assessed to determine if subjects meet the criteria for inclusion in each analysis population prior to releasing the database, and classifications will be documented per standard operating procedures.

### 4.1. Safety Analysis Set

The safety population will include all subjects who receive 1 dose of study vaccine. The safety population will be the only analysis population for the primary endpoints.

For local reactions, systemic events, fever, and use of antipyretic/pain medication, the definition of the denominators for the percentage calculations will be described in [Section 6.1.1.1](#) based on electronic diary (e-diary) record. In addition, these tables will be generated without e-diary data that have been confirmed by the subject to have been entered in error. Data-entry errors will be discussed in the clinical study report text and documented in a separate listing.

### 4.2. All-Available Immunogenicity Population

The all-available immunogenicity population will include all subjects who were enrolled, received the study vaccine, and had at least 1 valid and determinate assay result (OPA titer or IgG concentration) for at least 1 serotype 1 month after vaccination.

### 4.3. Evaluable Immunogenicity Population

The evaluable immunogenicity population will include subjects who meet the following:

1. Were eligible for the study based on the inclusion and exclusion criteria.
2. Received the study vaccine.
3. Received no prohibited vaccines.

4. Had blood drawn within the specified time frame 1 month after vaccination (28 to 42 days after Visit 1 (ie, Day 29 to Day 43 when Day 1 is vaccination visit).
5. Had at least 1 valid and determinate assay result (OPA titer or IgG concentration) for at least 1 serotype 1 month after vaccination.
6. Had no major protocol violations as determined by the sponsor's clinician, or any other protocol deviations that may materially affect assessment of immunogenicity endpoints.

#### 4.4. Other Analysis Sets

N/A.

### 5. GENERAL METHODOLOGY AND CONVENTIONS

All analyses will be performed after completion of the study.

#### 5.1. Hypotheses and Decision Rules

N/A. The study will be assessed by descriptive statistics.

#### 5.2. General Methods

##### 5.2.1. Analyses for Binary Data

Descriptive Summary:

The following statistics will be presented: number and percentage of subjects. The 2-sided 95% confidence interval (CI) will be also produced, if necessary.

Estimations:

#### Proportion

The CI for a single proportion will be computed using the F distribution. If  $r$  equals the number of responses and  $n$  equals the number of subjects, then it follows that  $p = r / n$  is the estimate of the proportion of responses. An exact 95% CI can be computed by solving the following 2 equations.

For the lower limit,  $p_L$ , use 
$$p_L = \frac{rF_L}{(rF_L + (n - r + 1))}$$

and

for the upper limit,  $p_U$ , use 
$$p_U = \frac{rF_U}{(n - r) + (r + 1)F_U}$$

where  $F_L$  is the quantile from the F distribution for  $\alpha = 0.025$ , with numerator degrees of freedom equal to  $2r$  and denominator degrees of freedom equal to  $2(n-r+1)$  and  $F_U$  is the quantile from the F distribution for  $\alpha = 0.975$ , with numerator degrees of freedom equal to  $2(r+1)$  and denominator degrees of freedom equal to  $2(n-r)$ .

When  $r$  equals 0,  $F_L$  should be set equal to 1.0 so  $p_L$  equals 0. When  $r$  equals  $n$ ,  $F_U$  should be set equal to 1.0 so  $p_U$  equals 1. The resulting proportions will be multiplied by 100 for presentation in tables. See Collett (1991) for more details.

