9.4. Safety Analysis

Safety is the primary objective. The safety endpoints are local reactions, systemic events, and unsolicited AEs and SAEs. The proportion of subjects with local reactions and systemic events reported on any day within the 7 days following vaccination for the 6- to <18-year age group, or within the 14-day period for the 18- to <65-year age group, will be compiled. These proportions, with the associated 2-sided 95% Clopper-Pearson CIs, will be summarized for each age group (6 to <18 years old and 18 to <65 years old). Severities of local reactions and systemic events will also be descriptively summarized.

AEs will be categorized according to MedDRA and will be summarized for subjects of all ages. All summaries will show the number and percentage of subjects experiencing at least

1 event and the number of events. Additional summaries by AE severity or by vaccine relationship may be produced. In addition, AEs and SAEs will be summarized for each age group (6 to <18 years old and 18 to <65 years old).

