**Reporting Summaries:**

➤ Summary of Subjects Reporting Local Reactions by Maximum Severity Grade of the Reaction

The number of subjects reporting “yes” for at least 1 day or “no” for all days (these values are used as the denominators for the percentage calculations), number of subjects reporting at least 1 occurrence of the specified reaction or any reaction by the maximum severity grade, observed proportion of subjects, and their exact 2-sided CIs (Clopper and Pearson).

The above is repeated for moderate or severe reactions.

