**Reporting Summaries:**

➤ Adverse Events Reported After Study Vaccination

The sample size, number and percentage of subjects reporting at least 1 event of each preferred term, arranged by system organ class with the associated Clopper-Pearson 95% CI, and number of occurrences of the event.

090177e190dcce77\Approved\Approved On: 06-May-2019 11:24 (GMT)

The below summary tables will be generated in the same way as the summary above. For death, only number and percentage of subjects reporting death will be summarized:

- Related Adverse Events Reported After Study Vaccination
- Serious Adverse Events Reported After Study Vaccination
- Related Serious Adverse Events Reported After Study Vaccination
- Severe Adverse Events Reported After Study Vaccination
- Related Severe Adverse Events Reported After Study Vaccination
- Life-Threatening Adverse Events Reported After Study Vaccination
- Related Life-Threatening Adverse Events Reported After Study Vaccination
- Adverse Events Leading to Discontinuation Reported After Vaccination
- Related Adverse Events Leading to Discontinuation Reported After Vaccination
- Immediate Adverse Events Reported After Vaccination (Immediate adverse events stand for events occurred during 30-minutes postvaccination observation)
- Related Immediate Adverse Events Reported After Vaccination
- Deaths During the Study Period
- Related Deaths During the Study Period

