**Reporting Summaries:**

➤ Proportions of Subjects With OPA Titers  $\geq$  LLOQ

Number of subjects with determinate OPA titers to the specified serotype, number and proportion of subjects with an OPA titer  $\geq$  LLOQ to the specified serotype, and exact 2-sided CIs (Clopper and Pearson) based upon the observed proportion of subjects.

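### The SAP's equation for the exact upper confidence limit has r where r + 1 is needed: coded as printed, every upper limit is too low, and it is 0 when no event is seen

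*SAP*

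**What the plan says.** Protocol 9.4 requires the proportions with local reactions and systemic events to be reported "with the associated 2-sided 95% Clopper-Pearson CIs". SAP 6.1.1.1 repeats this for local reactions ("observed proportion of subjects, and their exact 2-sided CIs (Clopper and Pearson"), and its rules carry over to systemic events, fever and antipyretic/pain medication use. SAP 6.1.1.5 does the same for adverse events ("arranged by system organ class with the associated Clopper-Pearson 95% CI"). SAP 6.2.1 uses the method for OPA titers at or above the LLOQ ("exact 2-sided CIs (Clopper and Pearson) based upon the observed proportion of subjects") and for 4-fold rises in OPA; 6.2.2 extends the 4-fold-rise rule to IgG.

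The only computational definition is in SAP 5.2.1, under Proportion: "An exact 95% CI can be computed by solving the following 2 equations". With r responders among n subjects, it gives:

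- lower limit: p_L = r F_L / (r F_L + (n − r + 1)), with F_L the 0.025 quantile of F on 2r and 2(n − r + 1) degrees of freedom;
- upper limit: p_U = r F_U / ((n − r) + (r + 1) F_U), with F_U the 0.975 quantile of F on 2(r + 1) and 2(n − r) degrees of freedom.

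For r = n, the section says that F_U "should be set equal to 1.0 so $p_U$ equals 1".

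**The concern.** The upper-limit equation has r in the numerator and r + 1 in the denominator, both multiplying the same F_U. That is not the Clopper-Pearson limit, and it does not return the boundary value stated a few lines below it.

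Safety is the primary objective, and SAP 5.1 rules out hypotheses and decision rules. The intervals are therefore the only statement of uncertainty about the primary proportions. For a rare reaction the upper limit carries the information, since it says how frequent the reaction could still be. The error always lowers that limit, and most strongly at 0 to 3 events. Protocol Table 6 discusses the study size in terms of incidences of 1% to 5%, so low counts are expected.

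**Working it through.** **Inputs.** The equations, quantiles and degrees of freedom are those of SAP 5.2.1. Sample sizes are 50 (6 to <18 years), 150 (18 to <65 years) and 200 in total, from protocol 3.3. The smallest age-category minimum there is 15.

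**Step 1: the SAP's own boundary value.** Put r = n and F_U = 1 into the printed equation:

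p_U = n / (0 + (n + 1)) = n/(n + 1)

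This is 50/51 = 0.980, 150/151 = 0.993 and 200/201 = 0.995, whereas the SAP says 1. With r + 1 in the numerator the result is (n + 1)/(n + 1) = 1.

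**Step 2: the correct form.** The Clopper-Pearson upper limit is the 0.975 quantile of a Beta(r + 1, n − r) distribution. If F has 2a and 2b degrees of freedom, aF/(b + aF) is Beta(a, b). Setting a = r + 1 and b = n − r gives

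p_U = (r + 1) F_U / ((n − r) + (r + 1) F_U)

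The SAP's degrees of freedom and denominator already match this; only the numerator does not. The printed limit is therefore r/(r + 1) times the correct one. With a = r and b = n − r + 1, the same identity reproduces the printed lower limit, which is right.

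**Step 3: worked cases.**

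- 0/50: the printed numerator is 0, so the limit is 0%. The exact limit is 1 − 0.025^(1/50) = 7.11%.
- 1/50: F_U on 4 and 98 degrees of freedom is 2.919. Printed: 2.919/(49 + 2 × 2.919) = 5.32%. Correct: 2 × 2.919/(49 + 2 × 2.919) = 10.65%.

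**Step 4: all counts.** Every r from 0 to n was run at n = 15, 50, 150 and 200 and compared with a standard exact routine. The printed upper limit was too low at every r. With r + 1 in the numerator, all upper limits agreed to rounding error (about 2 × 10⁻¹⁶), and the printed lower limits agreed equally closely.

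| Events | n = 50, printed / correct | n = 150, printed / correct | n = 200, printed / correct |
|---|---|---|---|
| 0 | 0% / 7.11% | 0% / 2.43% | 0% / 1.83% |
| 1 | 5.32% / 10.65% | 1.83% / 3.66% | 1.38% / 2.75% |
| 3 | 12.41% / 16.55% | 4.30% / 5.73% | 3.24% / 4.32% |
| 5 | 18.18% / 21.81% | 6.34% / 7.61% | 4.78% / 5.74% |
| 10 | 30.65% / 33.72% | 10.83% / 11.92% | 8.18% / 9.00% |
| n/2 | 61.99% / 64.47% | 57.50% / 58.26% | 56.57% / 57.13% |

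Local reactions are also tabulated by age category. There, 0/15 would show 0% instead of 21.8%.

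At r = n − 1 and r = n the printed limit falls below the observed proportion: 149/150 is 99.33% with a printed limit of 99.32% (correct 99.98%), and 50/50 has a printed limit of 98.04%. At r = n − 2 this no longer happens (48/50 is 96.0%, printed limit 97.5%).

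**Step 5: coverage**, summed exactly over the binomial distribution.

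| True incidence | n = 50, printed / correct | n = 150, printed / correct | n = 200, printed / correct |
|---|---|---|---|
| 1% | 38% / 99% | 76% / 98% | 85% / 98% |
| 2% | 62% / 98% | 79% / 99% | 89% / 96% |
| 5% | 91% / 99% | 93% / 96% | 91% / 97% |
| 10% | 86% / 97% | 93% / 97% | 95% / 97% |

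At 30% and 50% the printed interval covers 94.4% to 95.2%. The low values follow from the zero counts: since 0 events gives the interval [0%, 0%], coverage cannot exceed the chance of seeing at least one event. Protocol Table 6 puts that chance at 0.39, 0.78 and 0.87 for a 1% incidence. Those Table 6 figures reproduce (0.395, 0.779, 0.866) and are not affected by the error.

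**The case against.** The best defence is that the method is named wherever it is used. An exact Clopper-Pearson interval is fully determined, and a programmer who calls a standard exact routine never touches this fraction. SAP 5.2.1 also has the right quantiles, degrees of freedom, lower limit and boundary rule, and cites a textbook. On that view this is a typing slip that the boundary sentence exposes, in a descriptive study where no decision depends on an upper limit. For common reactions the factor r/(r + 1) is close to 1.

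A second point is that the equation was read from a text conversion of the SAP, in which a +1 could have been lost. The conversion did keep (r + 1) in the denominator and (n − r + 1) in the lower limit, but the issued page should be checked.

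Much of this stands. It is an error in the specification and does not show that any table is wrong; the loss is concentrated at low counts; and the interval excludes its own estimate only at r = n − 1 and r = n. None of it makes the equation right. SAP 5.2.1 says the interval will be computed from the F distribution, so a programmer and an independent validator who both follow it would agree on the same wrong limit.

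**Conclusion.** The concern holds. As printed, the upper-limit equation in SAP 5.2.1 is not the Clopper-Pearson limit required by protocol 9.4 and SAP 6.1.1.1, 6.1.1.5 and 6.2.1, and it contradicts the section's own value at r = n. If it is coded literally, every upper limit is understated by the factor r/(r + 1): to zero with no events, by half with one event, and by about 9% of its value with ten. Lower limits and point estimates are unaffected.

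Two conditions apply. The issued SAP must show the equation as read here, and the reported intervals are wrong only if the programs use it instead of a standard exact routine.

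**What to change.** In SAP 5.2.1, write the upper limit as p_U = (r + 1) F_U / ((n − r) + (r + 1) F_U), and keep the rule that p_U = 1 at r = n. Alternatively, drop the equations and refer only to the Clopper-Pearson method. Check the issued page first.

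Then confirm the table programs against a standard exact routine at r = 0, 1, n − 1 and n, for example at n = 15, 50, 150 and 200. Expected upper limits at r = 0 are 21.8%, 7.11%, 2.43% and 1.83%.

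The cost is one corrected line and one program check. Design, data and sample size do not change. If the printed equation had been coded, the corrected upper limits will be higher, most visibly for rare events.
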